### **9.1.5. Visit 4 – end of the DB phase (Day 56±7)**

Written below are the assessments to be completed at Visit 4 (either on site or remotely):

[figure not shown]
- Depression symptoms questionnaires:
  - By site qualified rater: HDRS21 (HDRS17- removing 4 last questions from the HDRS21), MDRS, CGI-S & CGI-I
  - By subject: QIDS-SR-16, Q-LES-Q. Subject self-reported questionnaire may be filled in electronically (ePRO) or by hard copy.
- Suicidal intent assessment by the investigator team (C-SSRS)
- Change in concomitant medications, if any.
- Significant change in health status, if any.
- Adverse events will be documented.
  - The characteristics of each subject study treatments regimen will be indicated on the subject binder.
  - At the end of the double-blind treatment phase treatment compliance would be verified as follows:
    - A stimulation session marked as “Pass” if a minimal average intensity of 25 on the Relivion®DP app (i.e= Minimal average stimulation of 2.57mA Trigeminal, and 6.92mA Occipital of the active stimulation), was delivered.
    - The first treatment week (Ramp Up) will not be counted for treatment compliance.
    - Expected treatment time for total DB phase: A total of 2400 minutes of “pass” treatment time (calculated as a scenario of 80 min per day, 5 days a week for 6 weeks).
    - Minimal patient compliance for the DB treatment period will be regarded as 70% compliance to the above cumulative “pass” stimulation time recommendation.
- DB treatment regimen compliant subjects will be offered to continue to the open label extension phase for additional 8±1 weeks.
- Treatment regimen non-compliant subjects will exit the study and return the device and iPhone, if provided. For these subjects this study visit would be the “end of study visit”.

- Once the OL treatment regimen allocation will be decided, the central trainer will contact the subject (on site or remote) to perform the device conversion to the open label mode (i.e. conversion of all devices to active mode), train the subjects on the assigned treatment regimen and re-train on the device use, if required.
- OL treatment regimens would include:
  - Maintenance treatment (for remitters): 40±10 minutes 3-4 times a week (intensity level up to 50)
  - Daily treatment (for responders): 5-7 days a week (intensity level up to 50) 60±20 minutes per day (preferably in two equal sessions of 30±10 minutes each).
  - Daily Intensified treatment regimen (for non-responders): 5-7 days a week (intensity level up to 60) 60±20 minutes per day (preferably in two equal sessions of 30±10 minutes each).
- Study visit 4 may occur during a 4 days period to allow for the HDRS response, treatment compliance assessments and OL treatment allocation to be finalized and data to be provided to the central trainer who may schedule a remote training session with the subject. In any case, the subject would continue his/her previous treatment regimen up until the day of the device conversion to the open label mode. The device conversion day would be considered as the first day of the OL treatment phase.
- Subjects which completed the minimal stimulation time required by the protocol will be considered as DB phase completers.

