## 6.3. Dosage Form

### 6.3.1. Double Blind Phase

For purposes of this study double blind phase, the Relivion®DP will be provided in therapeutic and non-therapeutic modes, to accommodate for the Active and Sham groups:

- Active Treatment: For the therapeutic mode the device will be preset to the following parameters: stimulation waveform- symmetrical biphasic, phase duration 130-300 microseconds, pulse frequency 80Hz, trigeminal stimulation intensity – up to 6.7mA, Occipital stimulation intensity – up to 18mA.
- Sham Control: For the non-therapeutic mode the device will be preset to the following parameters: Stimulation waveform- symmetrical biphasic, phase duration 100 microseconds, pulse frequency 0.33 Hz, trigeminal stimulation intensity up to 5mA, occipital stimulation intensity up to 10mA for 3 minutes, then gradually decrease to 0.2 mA and stays constant throughout the remaining treatment duration.

Both Active and Sham stimulation devices are packaged and labeled identically to maintain blinding of both the subject and study staff.

Double blind Relivion®DP treatment will last 60±20 minutes (preferably in two equal sessions of 30±10 minutes each) per day for 5-7 days a week (intensity level up to 50) for a period of 8±1 weeks.

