(visit 3) and at  $8\pm 1$  weeks post visit 2 (visit 4). During visits 3 and 4 subject's depression symptoms will be assessed by the site team qualified raters using the study questionnaires and the subject self-reported questionnaire. Study visit 4 will be the end of the double-blind phase and the beginning of the open label extension period. At this visit, subject's compliance with the treatment regimen during the DB phase will be assessed. Subjects who would not fulfill the minimum stimulation requirements during the DB phase (non-compliant subjects) will complete their participation in the study. DB phase treatment regimen compliant subjects will be offered to participate in a  $8\pm 1$  weeks open-label period with an active device. Subjects who choose to continue to the open label phase will be trained as per their recommended treatment regimen (see Figure 5) by the study central trainer in an on-site or remote fashion. (regardless their prior DB treatment assignment) and will follow this treatment regimen for the next 4-8±1 weeks. Subjects will return for follow up visits (on-site or remote) at  $4\pm 1$  weeks post visit 4 (visit 5) and at  $8\pm 1$  weeks post visit 4 (visit 6). During visits 5 and 6 subject's depression symptoms will be assessed by study team qualified raters and the PRO (electronic or hard copy) using the study questionnaires. At study visit 5 the subjects response to treatment, according to HDRS, will be re-evaluated and treatment regimen may be amended accordingly (see Figure 5), re-training will be performed by the central trainer, if required. Study visit 6 will be the end of study visit during which the device will be returned, final data will be collected, and the subjects will be exited from the study.

Subjects found ineligible by the procedures required at screening will be marked as 'screen failure' on the screening & enrollment log and will not take part in the study. Screen failure subjects will not be included in the intention-to-treat analysis, nor will they be counted as part of the target subject sample number.

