**Table 1: Schedule of Events**

Visit	Visit 1  Day -14-0	Visit 2  Day -4 -0	Visit 3 Week 4±1	Visit 4 Week 8±1	Visit 5 Week 12±1	Visit 6 Week 16±1
Event	Screening	Randomization	Double blind phase - Daily Treatment		open label extension phase	
Event / Visit window	Day -14-0	Day -4-0	Day 28 ±7	Day 56±7	Day 84±7	Day 112±7
Written/electronic Informed Consent	X					
Preliminary Eligibility Assessment (SCID)	X					
Medical history & Demography	X	X				
Concomitant medication	X	X 	X 	X 	X 	X 
Suicidal intent assessment (C-SSRS)		X	X	X	X	X
ATRF/ATIF	X					
Eligibility assessment	X	X				
Depression symptoms questionnaires (HDRS, MADRS, QIDS- SR -16, CGI-S&CGI-I)		X	X	X	X	X
Quality of Life Enjoyment and Satisfaction Questionnaire (Q-LES-Q)		X		X		X
Pregnancy urine test 	X					
Enrollment & Randomization		X				
Device training (on site or remote)		X		X 	X 	
Device conversion (Sham → Active) & OL treatment regimen training				X		
Blinding assessment questionnaire		X				
Device logs verification 		X		X		X
Active / sham DB treatment 			X	X		
Open label extension treatment 					X	X
Subject impression questionnaire						X
Adverse events		X	X	X	X	X
End of study				X 		X

1 visit 1 & 2 can be performed same day

2 change in concomitant medications /medical history

3 For women of childbearing potential only

4 Optional

5 Device logs – Remotely

6 weekly QIDS-SR-16

7 For treatment regimen non-compliant patients

 Neurolief Brain Innovation	MOOD: CLINICAL INVESTIGATION PLAN	Doc No.: CL-CIP-201 Rev: REV.3 / 09June2021 Pg. 46 of 92
--	--	--

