### **9.1.3. Daily treatment period (Day 0- day 56±7)**

- Subjects will operate the device along with the dedicated mobile application independently at home or surrounding, according to the recommended treatment regimen provided by the central trainer and on the “Relivion®DP quick guide” for 8±1 consecutive weeks. The Relivion®DP programmed treatment duration will be 40 minutes. The daily treatment (duration and intensity) will be gradually increased up to a full effective treatment of 60±20 minutes, 5-7 days a week. In general, it is expected that the recommended daily treatment time would be performed in two equal time sessions per day (e.g. morning and evening, each of about 30±10 minutes). During a treatment session, if necessary, treatment can be paused by the subject and then be resumed. Subjects will continue their daily treatment up to their scheduled visit 4 day.
- Subject will self-complete the QIDS-SR-16 once every 7 days starting from day 0 (electronic or hard copy).
- Study central trainer will periodically verify device logs on the study cloud database and may contact the subject for re-training, if required.
- Study team and central trainer will contact the subject periodically to remind him/her to use the device, if necessary.
- The summary of each subject study treatments will be indicated on the subject binder.
- During this period, subject will be asked to schedule 2 follow-up evaluation visits.

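### The Visit 4 minimum of 1,680 minutes cannot be reached at the low corner of the permitted regimen, so a subject within the written regimen can be classed as non-compliant

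*Protocol*

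**What the plan says.** The double-blind dose appears twice in the protocol. Section 6.3.1 says that "treatment will last 60±20 minutes (preferably in two equal sessions of 30±10 minutes each) per day for 5-7 days a week", for 8±1 weeks. Section 9.1.3 says that daily treatment "will be gradually increased up to a full effective treatment of 60±20 minutes, 5-7 days a week". Both permit 40 to 80 minutes a day.

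Section 9.1.5 sets the compliance rule. A session qualifies if its average intensity is at least 25. The expected qualifying time is 2,400 minutes, "calculated as a scenario of 80 min per day, 5 days a week for 6 weeks". Next, "Minimal patient compliance for the DB treatment period will be regarded as 70% compliance" with that total. Also, "The first treatment week (Ramp Up) will not be counted for treatment compliance".

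The consequence is stated in three places:
- Section 9.1.5: "Treatment regimen non-compliant subjects will exit the study and return the device and iPhone, if provided".
- Section 8.2: "Subjects who would not fulfill the minimum stimulation requirements during the DB phase (non-compliant subjects) will complete their participation in the study".
- Table 1: an end-of-study mark at Visit 4, footnoted "For treatment regimen non-compliant patients".

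Section 12.7.2 makes the same minimal stimulation time a condition for mITT. Protocol Section 12.7.5 and SAP Section 10.5 make mITT the principal efficacy set.

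**The concern.** The expected total is built from 80 minutes, the top of the daily range, while the regimen reaches down to 40. A 70% allowance on the top of the range does not stretch to half of it. The total is also fixed, whereas the counted period varies with the date of Visit 4.

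If the low corner of the regimen falls short, a subject can do what the protocol permits and still be labelled non-compliant. That subject is not offered open-label active treatment and is not counted as having completed the double-blind phase. Under Section 12.7.2 the subject also drops out of the set on which the primary result rests. A rule that decides membership of that set should not contradict the regimen it measures.

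**Working it through.** **Inputs.** Daily time 40 to 80 minutes, 5 to 7 days a week, 8±1 weeks (Sections 6.3.1 and 9.1.3). Scenario of 80 minutes, 5 days and 6 weeks; 70% fraction; first week uncounted (Section 9.1.5). Every session is assumed to meet the intensity condition.

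**The plan's own figure.** 80 × 5 × 6 = 2,400 minutes, as printed. The threshold is 0.70 × 2,400 = 1,680 minutes; it is not printed but follows directly.

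**Counted weeks.** 8±1 weeks gives 7, 8 or 9. Less the ramp-up week, 6, 7 or 8 count (Visit 4 on Day 49, 56 or 63).

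| | 6 counted weeks | 7 counted weeks (scheduled) | 8 counted weeks |
|---|---|---|---|
| 40 min × 5 days × weeks | 1,200 | 1,400 | 1,600 |
| as a share of 2,400 | 50.0% | 58.3% | 66.7% |
| shortfall against 1,680 | 480 | 280 | 80 |
| min/day needed at 5 days: 1,680 ÷ (5 × weeks) | 56 | 48 | 42 |
| min/day needed at 6 days: 1,680 ÷ (6 × weeks) | 46.7 | 40 | 35 |
| min/day needed at 7 days: 1,680 ÷ (7 × weeks) | 40 | 34.3 | 30 |
| nominal use: 60 min × 5 days × weeks | 1,800 | 2,100 | 2,400 |

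**Reading the table.** At 5 days a week, permitted use fails below 56, 48 or 42 minutes. At 6 days a week it fails only with 6 counted weeks, below 46.7 minutes. At 7 days a week it never fails. Nominal use passes in every window.

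**Could other wording rescue the low corner?**
- *Counting the ramp-up week.* Even at the full 40 minutes, the scheduled visit gives 40 × 5 × 8 = 1,600, still short.
- *The four-day Visit 4 period.* Section 9.1.5 lets Visit 4 spread over four days while the subject keeps treating. Four more 40-minute days give 1,200 + 160 = 1,360, 1,400 + 160 = 1,560 and 1,600 + 160 = 1,760. Only the last exceeds 1,680, and only if the period runs past Day 63 and those minutes count.

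**The case against.** The strongest reply is that 1,680 is a deliberate exposure floor, separate from the daily tolerance. This has force. Sections 8.2, 9.1.5 and 12.7.2 all refer to a minimum stimulation requirement, so it would be wrong to say that the protocol states no floor. The 80 minutes also has a natural source: the programmed session is 40 minutes, and Section 9.1.3 expects two sessions a day. But two sessions are a preference in Section 6.3.1 and a general expectation in Section 9.1.3, not a requirement. One full programmed session on each of five days is within the text and fails. Neither dosing section warns that permitted use may fall below the floor.

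A second reply is that subjects follow the central trainer and the quick guide, which are not in the documents and may recommend more than the minimum. If they do, few or no subjects meet the conflict. That bears on how often it arises; it does not make the protocol sections agree.

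A third reply is that the damage is contained, and most of this stands. The Visit 4 assessments include the HDRS, so the primary outcome should be available for a subject who then exits. The threshold is the same in both arms. SAP Section 7 repeats the primary analysis on ITT, which does not depend on the threshold. PP gives no such cover, because the protocol draws it from mITT. None of this restores open-label access.

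A reader might go further and infer an arithmetic error, or a biased primary result. The documents support neither: 2,400 and 70% of it are correct, and nothing shows how many subjects fell in the corner or in which arm.

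**Conclusion.** Wrong as written: an internal inconsistency, not a calculation error. The minimum in Section 9.1.5 is out of reach at 40 minutes on 5 days a week in all three windows, by 480, 280 or 80 minutes. At the scheduled Visit 4 the conflict is confined to use under 48 minutes a day on exactly 5 days a week.

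The conclusion rests on reading 60±20 minutes on 5 to 7 days as the permitted range, and on every session qualifying on intensity. The step to mITT rests on protocol Section 12.7.2. The SAP prevails over the protocol and its own mITT definition is not visible, although its mYITT definition (SAP Section 10.4) carries the same stimulation-time condition. The number of subjects affected is unknown and may be zero.

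**What to change.** **Wording.** Keep 1,680 minutes and say in Section 9.1.5 that it is a cumulative dose floor. State in Sections 6.3.1 and 9.1.3, and in the subject instructions, the minimum use that reaches it. At 5 days a week, 56 minutes covers every visit window (56 × 5 × 6 = 1,680), and 48 minutes suffices at the scheduled visit (48 × 5 × 7 = 1,680).

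**Subjects already treated.** Before unblinding, count from the device logs those who stayed within 40 to 80 minutes on 5 to 7 days a week yet fell below 1,680, using a rule written down in advance. After unblinding, report the count by arm and add one sensitivity run of the primary model with these subjects included. The 1,680-minute mITT stays principal. If the count is zero, the point closes.

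**Not recommended.** Lowering the threshold to match the regimen minimum would also remove the conflict, but it would loosen the principal efficacy set after the interim analysis reported in SAP Section 2.2.1.

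**Cost.** Slightly tighter regimen wording, one pass through logs that Section 9.8 says are recorded automatically, and one extra model run. SAP Section 6 says the treatment code was unrevealed up to SAP finalization; that it is still closed is an assumption. Exits already made cannot be reversed, and the wording change helps only subjects not yet treated.

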#### 9.1.6. Open label extension phase (Day 56±7- day 112±7)

- According to their visit 4 HDRS response assessment, subjects will be assigned into one of three open label treatment groups: Remitters/Responders/Non responders as follows:
  - Remitters: HDRS ≤7 at study visit 4 (week 8±1 post treatment initiation).
  - Responders: 50% ≥ HDRS score improvement from baseline at study visit 4 (week 8±1 post treatment initiation).
  - Non-responders: all other subjects who are not remitters or responders (50% <HDRS score improvement from baseline) at study visit 4 (week 8±1 post treatment initiation).

See Figure 5: Open label phase study flow.

 Neurolief Brain Innovation	MOOD: CLINICAL INVESTIGATION PLAN	Doc No.: CL-CIP-201 Rev: REV.3 / 09June2021 Pg. 50 of 92
--	--	--

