#### 5.1.2. Secondary Objectives

1. To assess the proportion of subjects achieving at least 50% improvement ("responders") in the HDRS17 score from baseline to 8 weeks post treatment initiation when using the Relivion®DP device compared to sham stimulation (Relivion®DP-Sham), in subjects suffering from MDD.
2. To assess the proportion of subjects achieving remission (HDRS17 score ≤7) at the 8 weeks post treatment initiation when using the Relivion®DP device compared to sham stimulation (Relivion®DP-Sham), in subjects suffering from MDD.

 Neurolief Brain Innovation	MOOD: CLINICAL INVESTIGATION PLAN	Doc No.: CL-CIP-201 Rev: REV.3 / 09June2021 Pg. 24 of 92
--	--	--

3. To assess the change in depressive symptoms, from baseline to 8 weeks post treatment initiation when using the Relivion®DP device compared to sham stimulation (Relivion®DP-Sham), in subjects suffering from MDD. Depressive symptoms severity will be assessed by the MADRS depression scale total score.

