### **5.1.6. Secondary Efficacy Endpoints**

1. Proportion of responder subjects- defined as the percent of subjects achieving at least 50% reduction from baseline in their HDRS17 scale 8 weeks post Relivion®DP treatment initiation.
2. Proportion of subjects achieving remission- defined as the percent of subjects with HDRS17 score≤7 at 8 weeks post Relivion®DP treatment initiation.
3. Mean change in depressive symptoms, measured by MADRS total score, from baseline to week-8 post treatment initiation.

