### 6.3.2. Open Label Phase

For purposes of the active open label phase, only active treatments will be applied with the Active therapeutic mode device parameters, as detailed above: stimulation waveform- symmetrical biphasic, phase duration 130-300 microseconds, pulse frequency 80Hz, trigeminal stimulation intensity – up to 6.7mA, Occipital stimulation intensity – up to 18mA.

The designated study central trainer will perform (on site or remote) the device conversion to the open label mode (i.e. conversion of the sham devices to active) with the subjects.

Open label phase treatment regimens would be as follows, according to the subject HDRS score at the end of the double-blind phase, for a period of 8±1 weeks:

**Maintenance treatment (for HDRS remitter subjects):** 40±10 minutes 3-4 times a week (intensity level up to 50).

**Daily treatment (for HDRS responder subjects):** 5-7 days a week (intensity level up to 50) 60±20 minutes per day (preferably in two equal sessions of 30±10 minutes each).

 Neurolief Brain Innovation	MOOD: CLINICAL INVESTIGATION PLAN	Doc No.: CL-CIP-201 Rev: REV.3 / 09June2021 Pg. 28 of 92
--	--	--

**Intensified treatment regimen (for HDRS non-responder subjects):** 5-7 days a week (intensity level - up to 60) 60±20 minutes per day (preferably in two equal sessions of 30±10 minutes each).

The treatment regimen assignment will be re-evaluated according to the subject HDRS score at visit 5 (after 4 weeks of open label treatment).

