**Figure 3: Device placement**

The user then presses on the water release covers located on the occipital electrodes to release moisture towards the scalp. To initiate treatment, the user presses the “+” button on the Relivion®DP. The indicator light begins flashing blue and electrical stimulus is applied. To increase the treatment intensity, the user presses the “+” button until he/she feels a tingling sensation over the forehead and occiput.

The user can further fine-tune the treatment intensity level by pressing the “+” or “-” buttons. The treatment automatically ends after 40 minutes or alternatively, the user can stop the treatment by turning the device off.

During use of the Relivion®DP the user can observe usage information via the application on the mobile phone. The mobile application displays the device status and provides indications and alerts such as treatment intensity level, treatment duration, low battery, charging state, etc. The device cannot be controlled (activate, adjust intensity, etc.) by the mobile application.

Detailed instructions for use of the Relivion®DP and the mobile app are provided in the User Manual.

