8.2 Secondary Efficacy Endpoints

Secondary efficacy endpoints include:

- **Proportion of responder subjects** - defined as the percent of subjects achieving at least 50% reduction from baseline in their HDRS-17 total score, 8 weeks post Relivion®DP treatment initiation.

- **Proportion of subjects achieving remission** - defined as the percent of subjects with HDRS-17 score≤7 at 8 weeks post Relivion®DP treatment initiation.
- **Change from baseline** to week-8 post Relivion®DP treatment initiation **in depressive symptoms** as measured by **MADRS** total score.

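### Protocol 9.1.6 prints both open-label allocation inequalities the wrong way round; very probably a notation slip, with effect limited to the intensity ceiling

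*Protocol*

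**What the plan says.** Protocol 9.1.6 sorts subjects into three open-label groups at Visit 4. Remitters have an HDRS score of 7 or less. The next group is printed as "Responders: 50% ≥ HDRS score improvement from baseline at study visit 4". The last is "all other subjects who are not remitters or responders (50% <HDRS score improvement from baseline". Section 9.1.7 refers back to 9.1.6 and Figure 5 for the re-evaluation at Visit 5, so the same rule is used twice.

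Response is defined in words elsewhere:

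- Protocol 5.1.2: "proportion of subjects achieving at least 50% improvement ('responders') in the HDRS17 score from baseline".
- Protocol 5.1.6: "percent of subjects achieving at least 50% reduction from baseline in their HDRS17 scale".
- SAP 8.2: "percent of subjects achieving at least 50% reduction from baseline in their HDRS-17 total score".

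Protocol 6.3.2 sets the regimen "according to the subject HDRS score at the end of the double-blind phase" and names the strongest one "Intensified treatment regimen (for HDRS non-responder subjects". Sections 6.3.2 and 9.1.5 give the regimen attached to each group but no percentage cut-offs.

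**The concern.** The two printed inequalities contradict the response definition used everywhere else. Taken literally, a subject who got worse is a responder, and a non-remitter who improved by 60% is a non-responder due for intensified stimulation.

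This is an operative rule: it sets a device intensity ceiling at Visit 4 and again at Visit 5. In the text available, 9.1.6 is the only place where the cut-offs appear inside the allocation rule. The SAP takes precedence where the two documents differ, but its design section (2.2.1) gives no cut-offs for the open-label groups, so it does not repair the error.

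Section 9.1.6 also says only HDRS, while 9.1.5 has both the 21-item and 17-item versions scored at the visit. A subject with an HDRS17 of 7 and any points on the last four items is a remitter on one version and not on the other.

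**Working it through.** The plan gives no figure to reproduce here; the check is one of logic.

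**Inputs.** The printed rule is from Protocol 9.1.6, the intended rule from Protocol 5.1.2 and 5.1.6 and SAP 8.2, and the regimens from Protocol 6.3.2 and 9.1.5. Baseline values are assumed for illustration.

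**Rules.** Let B be the baseline score, s the Visit 4 score, and improvement = (B − s)/B. Both rules first assign s ≤ 7 to remission. Among the rest:

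- Intended: responder if (B − s)/B ≥ 0.5, otherwise non-responder.
- As printed: responder if (B − s)/B ≤ 0.5, otherwise non-responder.

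The two can agree only where (B − s)/B = 0.5, that is, s = B/2.

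**Example, B = 24.**

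| Visit 4 score | Improvement | Intended group (ceiling) | Printed group (ceiling) |
|---|---|---|---|
| 8 to 11 | 16/24 = 66.7% down to 13/24 = 54.2% | Responder (50) | Non-responder (60) |
| 12 | 12/24 = 50.0% | Responder (50) | Responder (50) |
| 13 or more | 11/24 = 45.8% or less, including worsening | Non-responder (60) | Responder (50) |

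**Other baselines.** B = 20 gives agreement only at s = 10. B = 25 gives none, because s = 12 is 52% and s = 13 is 48%. For every integer B from 17 to 40, there is one agreeing score if B is even and none if B is odd.

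**What changes in treatment.** Responder and non-responder regimens are both 5–7 days a week and 60±20 minutes a day. Only the ceiling differs, 50 against 60. Below the ceiling the subject sets the level: "The user can further fine-tune the treatment intensity level by pressing" the plus or minus button (Protocol 6.8). The remitter regimen is unaffected, because its cut-off is printed correctly.

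**What changes in analysis.** The double-blind endpoints carry their own definitions and do not use 9.1.6. In SAP 11.5.7, the Visit 4 to Visit 6 comparison and the new-responder and new-remitter proportions select on absence of remission at Visit 4, which is the same under either reading. A wrong ceiling could reach the exploratory open-label outcomes only indirectly, through the treatment received.

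**Is it just number-first shorthand?** Inclusion criterion 5 also writes a number before the sign, 4 ≥ ATRF ≥ 1, and explains it in words as one to four adequate trials. There the signs carry their ordinary meaning. By that usage, 50% ≥ improvement means improvement of at most 50%.

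**The case against.** The strongest reply is that nobody would apply the literal rule. If the sign is read as a qualifier on the number before it (50% or more; less than 50%), both lines match the worded definition. The non-responder line also describes that group in words as everyone left over, and the intensified regimen is plainly meant for those who did not respond. Figure 5, cited alongside 9.1.6 for the allocation, is not shown in the available text and may be right. The SAP is dated May 2024 and speaks of open-label treatment in the past tense, so an edit now would probably change no allocation. The score ranges above describe a rule that may never have been used.

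Most of this stands. It makes a slip the probable explanation and limits the consequence. It does not make the printed text correct: the shorthand reading conflicts with how the protocol writes such an inequality in criterion 5, and a threshold that sets a stimulation ceiling should not need to be inferred from other sections. That allocation is probably complete moves the useful part of the remedy to the study report.

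On the scale name, HDRS17 is the natural reading, because the 7-point and 50% cut-offs are defined on it. Stating it costs nothing, and at the remission boundary the whole regimen depends on it: 3–4 times a week for 40±10 minutes, or 5–7 days a week for 60±20 minutes.

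**Conclusion.** The concern holds. Both inequalities in Protocol 9.1.6 are wrong as written, and followed literally they would swap the ceilings of 50 and 60 for every non-remitter except one with exactly 50% improvement. Confidence in the reversal is high, and it does not depend on the assumed baselines, which serve only as illustration.

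The impact is low. It is confined to the open-label intensity ceiling; no double-blind result and no SAP 11.5.7 analysis set changes. The documents give no evidence that any subject was allocated by the literal rule. The point should be corrected, but it does not threaten the trial's conclusions.

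**What to change.** Restate the groups in 9.1.6 as:

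- Remitters: HDRS17 ≤ 7.
- Responders: reduction from baseline HDRS17 of at least 50%, without remission.
- Non-responders: reduction from baseline HDRS17 of less than 50%, without remission.

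Check that Figure 5 says the same. In the study report, add one sentence stating which rule was actually applied at Visits 4 and 5.

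The cost is two signs, the scale name, a look at one figure and one sentence. No new data are needed and patients bear no cost.
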